10.1.5. Data protection

- Participants will be assigned a unique identifier by the investigator. Any participant records or datasets that are transferred to the sponsor will contain the identifier only; participant names or any information which would make the participant identifiable will not be transferred.
- GSK will ensure protection of the personal data of the investigator and site staff which is collected within the framework of and for the purpose of the study.
- The participant must be informed that their personal study-related data will be used by the sponsor in accordance with local data protection law. The level of disclosure must also be explained to the participant, that their data will be used as described in the informed consent.
- The participant must be informed that their medical records may be examined by Clinical Quality Assurance auditors or other authorized personnel appointed by the sponsor, by appropriate IRB/IEC members, and by inspectors from regulatory authorities.
- The contract between sponsor and study sites specifies responsibilities of the parties related data protection, including handling of data security breaches and respective communication and cooperation of the parties.
- Information technology systems used to collect, process, and store study-related data are secured by technical and organizational security measures designed to protect such data against accidental or unlawful loss, alteration, or unauthorized disclosure or access. GSK, third parties working on behalf of GSK, and/or institutions working with GSK for the purposes of this study are contractually bound to protect participant coded data. GSK will protect participant coded data and will only share it as described in the ICF.
- GSK has a global, internal policy that requires all GSK staff and complementary workers to report data incidents or breaches immediately, using dedicated tools. Clear procedures are defined for assessing and investigating data breaches to identify and to take appropriate remediation steps, to contain and to mitigate any risks for individuals resulting from a breach, in compliance with applicable laws.

10.1.6. Committees structure

A SRT is in place for each GSK product. It comprises of a global cross-functional team responsible for the ongoing assessment of benefit-risk for a product. The SRT contribute to the continual assessment of incoming new efficacy and safety information.

10.1.7. Dissemination of Clinical Study Data

- The key design elements of this protocol and results summaries will be posted on www.ClinicalTrials.gov and/or GSK Clinical Study Register in compliance with applicable regulations/GSK policy. GSK will aim to register protocols summaries prior to study start and target results summaries submission within 12 months of primary/ study completion date. Where external regulations require earlier disclosure, GSK will follow those timelines.
- Where required by regulation, summaries will also be posted on applicable national or regional clinical study registers.
- Where required by applicable regulatory requirements, an investigator signatory will be identified for the approval of the study report, and provided reasonable access to statistical tables, figures, and relevant reports. GSK will also provide the investigator with the full summary of the study results, including a summary of trial results understandable to laypersons. The investigator is encouraged to share the plain language summary with the study participants, as appropriate. The full study report will be made available upon request, after decision on marketing authorization by regulatory authorities.
- Where required by regulation, the names of the sponsor signatory and investigator signatory will be made public.
- GSK will provide the investigator with the participant-level line listings for their site only after completion of the full statistical analysis.
- GSK intends to make anonymized participant-level data from this study available to external researchers for scientific analyses or to conduct further research that can help advance medical science or improve patient care. This helps ensure the data provided by study participants are used to maximum effect in the creation of knowledge and understanding. Data will be shared with researchers in a non-identifying way, and appropriate measures will be taken to protect PI; these measures will comply with data protection and privacy laws that apply.

10.1.8. Data quality assurance

- All participant data relating to the study will be recorded on printed or electronic CRFs unless transmitted to the sponsor or designee electronically (e.g., laboratory data). The investigator is responsible for verifying that data entries are accurate and correct by physically or electronically signing the CRF.
- Guidance on completion of eCRFs will be provided in eCRF completion guidelines.
- The investigator must permit study-related monitoring, audits, IRB/IEC review, and regulatory agency inspections and provide direct access to source documents.
- QTLs will be predefined in the QTL Plan to identify systematic issues that can impact participant right, safety and/or reliability of study results. These predefined parameters will be monitored during the study, and important deviations from the QTLs and remedial actions taken will be summarized in the CSR.
- Monitoring details describing strategy, including definition of study critical data items and processes (e.g., risk-based initiatives in operations and quality such as risk management and mitigation strategies and analytical risk-based monitoring, involvement of central reading mechanism) methods, responsibilities, and requirements, including handling of noncompliance issues and monitoring techniques (central, remote, or on-site monitoring) are provided in the monitoring plan.
- The sponsor or designee is responsible for the data management of this study, including quality checking of the data.
- The sponsor assumes accountability for actions delegated to other individuals (e.g., contract research organizations).
- Records and documents, including signed ICF, pertaining to the conduct of this study must be retained by the investigator for a minimum period of 15 years from the issue of the final CSR/ equivalent summary, or in accordance with Applicable Law, whichever is longer. No records may be destroyed during the retention period without the written approval of the sponsor. No records may be transferred to another location or party without written notification to the sponsor.

10.1.9. Source documents

- For this study there will not be source data recorded directly into the eCRF (i.e., no prior written or electronic record of data is available).
- Source documents provide evidence for the existence of the participant and substantiate the integrity of the data collected. Source documents are filed at the investigator's site.
- Data reported on the eCRF or entered in the eCRF that are transcribed from source documents must be consistent with the source documents or the discrepancies must be explained. The investigator may need to request previous medical records or transfer records, depending on the study. Also, current medical records must be available.

- Definition of what constitutes source data and its origin can be found in e.g. source data acknowledgment.
- The investigator must maintain accurate documentation (source data) that supports the information entered in the eCRF.
- The sponsor or designee will perform monitoring to confirm that data entered into the eCRF by authorized site personnel are accurate, complete, and verifiable from source documents; that the safety and rights of participants are being protected; and that the study is being conducted in accordance with the currently approved protocol and any other study agreements, ICH GCP, and all applicable regulatory requirements.

10.1.10. Study and site start and closure

Start of study and first act of recruitment

The start of study and the first act of recruitment are defined as FSFV (first ICF signature date) at a country-level.

Study/site termination

GSK or designee reserves the right to close the study site or terminate the study at any time for any reason at the sole discretion of GSK. Study sites will be closed upon study completion. A study site is considered closed when all required documents and study supplies have been collected and a study site closure visit has been performed.

The investigator may initiate study site closure at any time, provided there is reasonable cause and sufficient notice is given in advance of the intended termination.

Reasons for the early closure of a study site by the sponsor or investigator may include but are not limited to:

For study termination:

- Discontinuation of further study intervention development

For site termination:

- Failure of the investigator to comply with the protocol, the requirements of the IRB/IEC or local health authorities, the sponsor's procedures, or GCP guidelines
- Inadequate or no recruitment (evaluated after a reasonable amount of time) of participants by the investigator
- Total number of participants included earlier than expected

If the study is prematurely terminated or temporarily suspended, the sponsor shall promptly inform the investigators, the IECs/IRBs, the regulatory authorities, and any contract research organization(s) used in the study of the reason for termination or temporary suspension, as specified by the applicable regulatory requirements. The

investigator shall promptly inform the participant and should assure appropriate participant therapy and/or follow-up.

10.1.11. Publication policy

GSK seeks to publish medically or scientifically significant results in searchable peer-reviewed scientific literature within 18 months from LSLV. We follow International Committee of Medical Journal Editors standards for authorship and use Good Publications practices to guide our publications.

10.2. Appendix 2: Clinical laboratory tests

- The tests detailed in [Table 7](#) will be performed by local laboratories.
- Protocol-specific requirements for inclusion or exclusion of participants are detailed in Section [5](#) of the protocol.
- Additional tests may be performed at any time during the study as determined necessary by the investigator or required by local regulations.
- Investigators must document their review of each laboratory safety report.

Table 9 Protocol-required safety laboratory tests

Laboratory Tests	Parameters	
Hematology	• Platelet count	
	• Red blood cell (RBC) count	
	• RBC indices	
 – Mean corpuscular volume (MCV) – Mean corpuscular hemoglobin (MCH) – %Reticulocytes
	• WBC count with differential:	
 – Neutrophils – Lymphocytes – Monocytes – Eosinophils – Basophils
	• Hemoglobin	
	• Hematocrit	

Laboratory Tests	Parameters
Serum chemistry*	
 • Blood urea nitrogen (BUN)/Urea • Potassium • Creatinine** • Sodium • Calcium • Glucose [indicate if fasting or non-fasting] • Creatine phosphokinase (CPK) • Serum Albumin Concentration • CCI [REDACTED] • CCI [REDACTED] • CCI [REDACTED]
Routine urinalysis	
 • Specific gravity • pH, glucose, protein, blood, ketones, [bilirubin, urobilinogen, nitrite, leukocyte esterase] by dipstick • Microscopic examination (if blood or protein is abnormal) 
 – Epithelial cells – Red Blood cells – WBC – Casts – Crystals
Coagulation testing	
 • Prothrombin Time • International normalized ratio • Activated partial thromboplastin

Laboratory Tests	Parameters
Additional tests	
 • HIV test • HBsAg (and DNA test, as applicable) • HBcAb • HCV (and RNA test for participants with HI, as applicable) • Urine drug screen- Opiates, Amphetamines, Cocaine, Cannabinoids • Breath alcohol screen • Serum/urine pregnancy test (for females only)*** • Serum FSH (for postmenopausal females only) • SARS-CoV-2 rapid test and/or polymerase chain reaction test

* Serum chemistry tests will be performed after at least an 8-hour fast; however, in case of dropouts or rechecks, participants may not have fasted for 8 hours prior to when the serum chemistry sample is taken.

** At the screening visit, creatinine clearance will be calculated using the Cockcroft-Gault formula.

*** At screening, pregnancy test will be performed in serum; other pregnancy test can be performed in serum or urine as per local guidelines.

10.3. Appendix 3: AEs and SAEs: Definitions and procedures for recording, evaluating, follow-up, and reporting

10.3.1. Definition of AE

AE definition

 • An AE is any untoward medical occurrence in a clinical study participant, temporally associated with the use of a study intervention, whether or not considered related to the study intervention. • NOTE: An AE can therefore be any unfavorable and unintended sign (including an abnormal laboratory finding), symptom, or disease (new or exacerbated) temporally associated with the use of a study intervention.
Events Meeting the AE Definition

 • Any abnormal laboratory test results (hematology, clinical chemistry, or urinalysis) or other safety assessments (e.g., ECG, radiological scans, vital signs measurements), including those that worsen from baseline, considered clinically significant in the medical and scientific judgment of the investigator (i.e., not related to progression of underlying disease). • Exacerbation of a chronic or intermittent pre-existing condition including either an increase in frequency and/or intensity of the condition.

- New condition detected or diagnosed after study intervention administration even though it may have been present before the start of the study.
- Signs, symptoms, or the clinical sequelae of a suspected intervention- intervention interaction.
- Signs, symptoms, or the clinical sequelae of a suspected overdose of either study intervention or a concomitant medication. Overdose per se will not be reported as an AE/SAE unless it is an intentional overdose taken with possible suicidal/self-harming intent. Such overdoses should be reported regardless of sequelae.
- Events that occur as a result of protocol-mandated procedures (i.e. invasive procedures, modification of participant's previous therapeutic regimen).

Events NOT Meeting the AE Definition

- Any clinically significant abnormal laboratory findings or other abnormal safety assessments that are associated with the underlying disease, unless judged by the investigator to be more severe than expected for the participant's condition.
- Medical or surgical procedure (e.g., endoscopy, appendectomy): the condition that leads to the procedure is the AE.
- Situations in which an untoward medical occurrence did not occur (social and/or convenience admission to a hospital, admission for routine examination.).
- Anticipated day-to-day fluctuations of pre-existing disease(s) or condition(s) present or detected at the start of the study that do not worsen. Pre-existing diseases will be recorded in the medical history section of the eCRF.
- Hospitalization for elective treatment of a pre-existing condition (known or diagnosed before signing the informed consent) that did not worsen from baseline.

10.3.2. Definition of SAE

An SAE is defined as any untoward medical occurrence that, at any dose, meets one or more of the criteria listed:

a. Results in death

b. Is life-threatening

The term 'life-threatening' in the definition of 'serious' refers to an event in which the participant was at risk of death at the time of the event. It does not refer to an event, which hypothetically might have caused death, if it were more severe.

c. Requires inpatient hospitalization or prolongation of existing hospitalization

- In general, hospitalization signifies that the participant has been admitted (usually involving at least an overnight stay) at the hospital or emergency ward for observation and/or treatment that would not have been appropriate in the physician's office or outpatient setting. Complications that occur during hospitalization are AE. If a complication prolongs hospitalization or fulfills any

An SAE is defined as any untoward medical occurrence that, at any dose, meets one or more of the criteria listed:

other serious criteria, the event is serious. When in doubt as to whether “hospitalization” occurred or was necessary, the AE should be considered serious.

- Hospitalization for elective treatment of a pre-existing condition that did not worsen from baseline is not considered an AE.
- d. Results in persistent or significant disability/incapacity
 - The term disability means a substantial disruption of a person’s ability to conduct normal life functions.
 - This definition is not intended to include experiences of relatively minor medical significance such as uncomplicated headache, nausea, vomiting, diarrhea, influenza, and accidental trauma (e.g., sprained ankle) that may interfere with or prevent everyday life functions but do not constitute a substantial disruption.
- e. Is a congenital anomaly/birth defect in the offspring of a study participant.
- f. Abnormal pregnancy outcomes (e.g., spontaneous abortion, fetal death, stillbirth,
- g. Is a suspected transmission of any infectious agent via an authorized medicinal product
- h. Other situations:
 - Possible Hy’s Law case: ALT $\geq 3x$ ULN AND total bilirubin $\geq 2x$ ULN ($>35\%$ direct bilirubin) or INR >1.5 must be reported as SAE
 - Medical or scientific judgment should be exercised by the investigator in deciding whether SAE reporting is appropriate in other situations such as significant medical events that may jeopardize the participant or may require medical or surgical intervention to prevent one of the other outcomes listed in the above definition. These events should usually be considered serious.
 - Examples of such events include invasive or malignant cancers, intensive treatment for allergic bronchospasm, blood dyscrasias, convulsions, or development of intervention dependency or intervention abuse.

10.3.3. **Solicited events**

Definition of solicited event

- Solicited AEs are predefined local systemic events for which the participant is specifically questioned.

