1. PROTOCOL SUMMARY

1.1. Synopsis

Protocol Title: A phase 1, open-label study to investigate the pharmacokinetics and safety of camlipixant in male and female participants aged 18-75 years of age with hepatic impairment compared to matched healthy participants with normal hepatic function.

Brief Title: A study to investigate the pharmacokinetics and safety of camlipixant in male and female healthy participants and participants with hepatic impairment aged 18-75 years of age.

Rationale:

As per the FDA hepatic guidance, a sponsor should evaluate the PK of its investigational drug in participants with HI when hepatic metabolism and/or excretion accounts for substantial portion (>20% of the absorbed drug) of the elimination of the parent or active metabolite. Camlipixant meets this criterion.

Camlipixant is primarily eliminated through liver metabolism, the main routes of metabolism are de-alkylation, oxidation, oxidation followed by glucuronidation, oxidation and ring opening, and oxidation to the carboxylic acid, de-methylation. Camlipixant is metabolized by CYP3A4, 2C8, 1A1 and 2D6 enzymes. Total camlipixant AUC is predicted to increase by approximately 1.4-fold in moderate HI participants and by 1.6-fold in severe HI participants compared to control participants with an increase of up to 3-fold for the unbound AUC in the severe category. The purpose of this study is to determine the effect of HI on the PK profile and safety of camlipixant. The data generated will provide guidance on the administration of camlipixant to participants with impaired hepatic function.

Objectives, Endpoints, and Estimands:

Objective(s)	Endpoint(s)
Primary	
To assess the effect of HI on the PK of camlipixant in participants with HI compared to healthy control participants.	AUC _(0-∞) and C _{max} .
Secondary	
To evaluate the safety and tolerability of camlipixant in participants with HI compared to healthy control participants.	Incidence of Adverse Events, Serious Adverse Events and Adverse Events of Special Interest. Incidence of participants with clinically relevant changes in clinical laboratory tests, ECG and vital signs assessments.
To assess the effect of HI on other PK parameters of camlipixant in participants with HI compared to healthy control participants.	T _{max} , t _{1/2} , CL/F, and Vz/F.
Exploratory	
CCI	

Primary Estimand:

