5.1.1.2. Additional inclusion criteria for healthy control participants

9. Medically healthy with no clinically significant medical history, physical examination, screening clinical laboratory profiles, vital signs and ECGs, as deemed by the PI or designee, including the following:
 - Seated blood pressure is $\geq 90/40$ mmHg and $\leq 140/90$ mmHg at the screening visit.
 - Seated heart rate is ≥ 40 bpm and ≤ 99 bpm at the screening visit.
 - QTcF interval is ≤ 450 msec and has ECG findings considered normal or not clinically significant by the PI or designee at the screening visit.
 - QTc ≤ 480 msec in participants with bundle branch block

NOTE:

- The QTc is the QT interval corrected for heart rate according to Fridericia's formula (QTcF). It is either machine-read or manually over-read.
- AST, ALT, direct bilirubin, indirect bilirubin, and total bilirubin within normal ranges at the screening visit and check-in. Only abnormal values up to 1.5 x upper limit of normal may be repeated once.

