7. DISCONTINUATION OF STUDY INTERVENTION AND PARTICIPANT DISCONTINUATION/WITHDRAWAL

7.1. Discontinuation of study intervention

As each participant receives a single dose of study intervention, later discontinuation of study drug is not possible. If an AE or other situation is identified, it is preferred for the participant to remain in the study for full evaluation per the SoA (Section 1.3).

If the participant experiences a liver event, refer to Section 10.6 for required Liver Safety Actions and Follow-up Assessments; the participant does not need to be withdrawn from the study.

The primary reason for premature discontinuation of the study intervention will be documented in the [CRF/eCRF] based on the list below:

Reasons	Additional items/Sub-reasons
Lost to follow-up	Participant Relocated Participant was Incarcerated Other, specify Unknown
Physician Decision	Specify Safety, behavioral
Protocol Deviation	Specify Incorrect dose Or dose not given
Site Terminated by Sponsor	
Study Terminated by Sponsor	
Withdrawal by Participant	Burden of Procedure Participant Relocated COVID-19 Other Unknown
Other	Specify
Death	

[figure not shown]

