10.6. Appendix 6: Liver safety: suggested actions and follow-up assessments

Phase 1 liver chemistry stopping criteria have been designed to assure participant safety and to evaluate liver event etiology.

Phase 1 Liver Chemistry Stopping Criteria and Required Follow-Up Assessments

Liver Chemistry Stopping Criteria – Liver Stopping Event	
Actions	Follow-Up Assessments

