
ALT-absolute
 
ALT\geq3xULN If ALT\geq3xULN AND total bilirubin^{1,2} \geq2xULN (for participants with known Gilbert's syndrome these criteria only apply if total bilirubin \geq2xULN, and direct bilirubin \geq2xULN and at least doubled from baseline value) or ALT\geq3xULN AND INR $>$1.5, report as an SAE.
 
MONITORING:
 
If ALT\geq3xULN AND total bilirubin \geq2xULN or INR $>$1.5:
 
 Repeat liver chemistries (include ALT, AST, alkaline phosphatase, total bilirubin and INR) and perform liver event follow-up assessments within 24 hours Monitor participant twice weekly until liver chemistries reduce to $<$3xULN for ALT, $<$2xULN for total bilirubin or \leq1.5 for INR or return to or remain within baseline or normal limits. A specialist or hepatology consultation is recommended 
If ALT\geq3xULN AND total bilirubin $<$2xULN and INR \leq1.5:
 
 Perform liver chemistries (include ALT, AST, alkaline phosphatase, total bilirubin and INR) and perform liver event follow-up assessments within 24-72 hours Monitor participant weekly until liver chemistries reduce to $<$3xULN for ALT or 	
 Viral hepatitis serology³. Anti-nuclear antibody, anti-smooth muscle antibody, Type 1 anti-liver kidney microsomal antibodies, and quantitative total immunoglobulin G (IgG) or gamma globulins. Obtain INR and recheck with each liver chemistry assessment until the aminotransferases values show downward trend. Obtain blood sample for pharmacokinetic (PK) analysis, 96 hr after the dose⁴. Obtain serum creatine phosphokinase (CPK), lactate dehydrogenase (LDH), gamma-glutamyl transferase (GGT), glutamate dehydrogenase (GLDH) and serum albumin. Fractionate bilirubin, if total bilirubin \geq2xULN. Obtain complete blood count with differential to assess eosinophilia. Record the appearance or worsening of clinical symptoms of liver injury, or hypersensitivity, on the liver event form. Record use of concomitant medications on the concomitant medications CRF page including acetaminophen, herbal remedies, recreational drugs and other over-the-counter medications. Record alcohol use on the liver event alcohol intake form. 
If ALT\geq3xULN AND total bilirubin \geq2xULN or INR $>$1.5 obtain the following in addition to the assessments listed above:

Liver Chemistry Stopping Criteria – Liver Stopping Event	

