ALT-absolute	ALT \geq 3xULN If ALT \geq 3xULN AND total bilirubin ^{1,2} \geq 2xULN (for participants with known Gilbert's syndrome these criteria only apply if total bilirubin \geq 2xULN, and direct bilirubin \geq 2xULN and at least doubled from baseline value) or ALT \geq 3xULN AND INR $>$ 1.5, report as an SAE.
Required Actions, Monitoring and Follow-up Assessments	
Actions	Follow-Up Assessments
return to or remain within baseline or normal limits.	
 Serum acetaminophen adduct assay should be conducted (where available to assess potential acetaminophen contribution to liver injury unless acetaminophen use is very unlikely in the preceding week (e.g., where the participant has been resident in the clinical unit throughout). Liver imaging (ultrasound, magnetic resonance, or computed tomography) to evaluate liver disease; complete liver imaging form. Liver biopsy may be considered and discussed with local specialists if available for instance: 
 In participants when serology raises the possibility of autoimmune hepatitis (AIH) In participants when suspected DILI progresses or fails to resolve on withdrawal of study intervention In participants with acute or chronic atypical presentation. If liver biopsy is conducted, then complete liver biopsy form

1. Serum bilirubin fractionation should be performed if testing is available. If serum bilirubin fractionation testing is unavailable, record presence of detectable urinary bilirubin on dipstick, indicating direct bilirubin elevations and suggesting liver injury.
2. All events of ALT \geq 3xULN and total bilirubin \geq 2xULN (for participants with known Gilbert's syndrome these criteria only apply if total bilirubin \geq 2xULN, and direct bilirubin \geq 2xULN and at least doubled from baseline value) or ALT \geq 3xULN and INR $>$ 1.5, which may indicate severe liver injury (possible 'Hy's Law'), must be reported as an SAE (excluding studies of hepatic impairment or cirrhosis); the INR threshold value stated will not apply to participants receiving anticoagulants.

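### Protocol 10.3.2(h) makes every possible Hy's Law case an SAE, but Appendix 6 footnote 2 lifts that duty for hepatic-impairment studies, which read literally includes this trial's healthy controls

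*Protocol*

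**What the plan says.** Two parts of the protocol give a reporting rule for the same liver event.

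- **Section 10.3.2(h)**, in the SAE definition: ALT at least 3xULN with total bilirubin at least 2xULN (more than 35% direct) "or INR >1.5 must be reported as SAE". No study type, cohort or baseline status is exempted.
- **Section 10.6, Appendix 6**: the table row says "report as an SAE", and its bilirubin term carries a reference to footnote 2. The footnote says such events "must be reported as an SAE (excluding studies of hepatic impairment or cirrhosis", and adds that "the INR threshold value stated will not apply to participants receiving anticoagulants".

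The trial's title describes a study in participants "with hepatic impairment compared to matched healthy participants with normal hepatic function". Under 5.1.1.2, controls need "AST, ALT, direct bilirubin, indirect bilirubin, and total bilirubin within normal ranges at the screening visit and check-in".

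For a liver event, Section 7.1 tells the site to "refer to Section 10.6 for required Liver Safety Actions and Follow-up Assessments", and 7.1.1 repeats the instruction. The appendix's own heading calls its content "suggested actions and follow-up assessments".

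**The concern.** The two rules give opposite answers for the same event in this trial. The exemption also attaches to the study rather than to the participant. Its evident rationale is that liver tests may already be abnormal before dosing, which 7.1.1 notes for participants with HI. That rationale does not apply to a control who entered with normal values, and in a control a possible Hy's Law pattern after dosing would be most informative about the drug.

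What is at stake is the expedited report. Section 8.4.1 requires SAEs to reach the sponsor within 24 hours. A site that relied on footnote 2 could leave that report out. The case would then also be missing from the SAE incidence, a descriptive secondary endpoint that SAP 4.5.2 tabulates by cohort.

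**Working it through.** The plan states no figure to reproduce. The check compares texts, with a short count at the end.

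**1. Does the footnote reach this trial, and its controls?** By its title this is a hepatic-impairment study, so the exclusion applies. It names studies, not participants with impairment, so read literally it covers the controls too.

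**2. Does it reach both limbs of the criterion?** In the table row the footnote mark sits on bilirubin only, but the footnote's own text restates the INR limb. Both are covered.

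**3. Does any text decide between the two rules?**

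| Place | Where it sends the reader | For what |
|---|---|---|
| Protocol 8.3.4 | 10.3.1 and 10.3.2 | whether an abnormal laboratory finding is an AE or SAE |
| Protocol 8.4 | 10.3 | safety definitions; completing and transmitting SAE reports |
| Protocol 8.4.1 | 10.3 | the 24-hour SAE duty |
| SAP 4.5.2 | Protocol 10.3 | SAE definition for analysis |
| Protocol 7.1, 7.1.1 | 10.6 (Appendix 6) | required liver actions and follow-up |

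Most pointers favour Section 10.3. None says that it prevails over Appendix 6 or that footnote 2 is to be disregarded.

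**4. Does either rule, taken literally, suit both populations?**

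- *Controls.* AST, ALT and bilirubin are normal at screening and check-in. Nothing in the documents supports exempting them.
- *HI participants.* Section 5.1.1.1 admits total bilirubin up to 6 mg/dL. In the Child-Pugh table (Table 3) the two-point INR band starts at 1.70, already above 1.5. Such a participant meets the INR limb before dosing, so ALT at or above 3xULN alone would complete the criterion. An unmodified 10.3.2(h) fits this group poorly.

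**5. Scale.**

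- SAP 4.6 limits Part 2 to severe HI. With 1:1 matching the plan is 8 + 8 + 8 + 8 = 32 participants, of whom 8 + 8 = 16 are controls.
- One omitted case in a cohort of 8 would lower its reported SAE incidence by 1/8 = 12.5 percentage points, provided that participant had no other SAE. This holds for any single missed event and says nothing about how likely one is.
- The documents give no event rate. The hepatic-effects entry of the risk assessment (2.3.1) reports ALT and AST above 3xULN at 200 mg BID or more, without a concurrent bilirubin rise. Participants here receive one 50 mg dose.

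**The case against.** The strongest reply is that the documents do divide the work: Section 10.3 settles SAE status and transmission, and Appendix 6 settles the liver work-up. Section 8.3.4 addresses abnormal laboratory findings directly and refers them to 10.3.2. The Appendix 6 row itself also tells the site to report. On this view one parenthetical stands against everything else. The amendment summary says text was added to Appendix 6 to match the sponsor's template, which is consistent with generic wording left in place, though it does not prove it.

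Much of this stands. A reader might infer that the site has no guidance at all. The documents do not support that, and a careful site would probably report. What remains is that the footnote is specific to this kind of study and sits where a site with a liver event is sent, and nothing cancels it.

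A reader might also infer that an omitted case would disappear. That is not supported either:

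- Appendix 6 monitoring still applies.
- SAP 4.5.3.1 and 4.5.3.1.1 list laboratory and liver data.
- SAP 6.2.1 flags these combinations.
- The medical-judgement clause in 10.3.2 remains open to the investigator.

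These would probably bring the case to light, but none guarantees a 24-hour report.

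Finally, an exemption for HI participants is defensible. Besides the baseline values allowed at entry, 10.3.1 already leaves out findings due to the underlying disease unless they are worse than expected. The defect lies mainly in the reach to controls.

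**Conclusion.** The inconsistency is real: for a possible Hy's Law case in a healthy control, 10.3.2(h) requires an SAE report and footnote 2, read literally, does not. The conclusion rests on that literal reading and on the absence of any precedence statement in either document.

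The likely effect is small. Few or no cases are expected, 16 controls are planned, and the primary PK objective is untouched. How many participants remain to be dosed cannot be told from the documents. Low to moderate priority.

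Two wording differences might be read as further reporting gaps, but they carry little weight. SAP 6.2.1 uses bilirubin above 2xULN where the protocol uses at or above, which differs only at equality and concerns a data flag rather than a site's duty. The direct-bilirubin condition appears in 10.3.2(h) and SAP 6.2.1 but not as a general condition in Appendix 6, so Appendix 6 is the broader trigger.

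**What to change.** In Appendix 6 footnote 2, replace the study-level exclusion with a participant-level rule:

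- *Healthy controls: every possible Hy's Law case is reported as an SAE under 10.3.2(h).*
- *HI participants whose baseline ALT, bilirubin or INR is outside the reference range: SAE status is judged against baseline, using the 10.3.1 test of whether the finding is worse than the condition would explain, and the baseline-specific limits in 7.1.1.*

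An HI participant with all three values in range at baseline then falls under the ordinary rule. The 7.1.1 limits do not include INR, so for INR the 10.3.1 judgement has to serve.

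Put the same sentence into 10.3.2(h), together with the Gilbert's syndrome and anticoagulant exceptions that now stand only in Appendix 6. Otherwise the two texts would still differ.

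Do not add the direct-bilirubin condition to Appendix 6, since that would narrow its trigger. The SAP threshold can be aligned at the next SAP revision.

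The cost is a few lines of text, with no new visits, samples or data. As a protocol amendment it needs the IRB/IEC and health authority approvals described in 10.1.1.
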